A total of 54 patients with the diagnosis of knee OA grade II and III will be recruited to receive a single intra-articular injection of MSC: Group 1 (n 18 patients) will receive BM-MSC and Group 2 (n 18 patients) will receive AD-MSC, and Group 3 (n 18 patients) will receive BM-MSC + AD-MSC.

a. Inclusion criteria:

- i. Patients aged 18 to 70 years, with grade II and III knee OA, according to the Ahlbäck classification will be included. Identified by two different observers.
- ii. Minimal VAS pain score of 4.
- iii. Chronic knee pain of mechanical origin.
- iv. All patients who sign a specially prepared informed consent for this clinical trial.

b. Exclusion criteria:

- i. Varus or valgus knee mal alignment superior to 10°.
- ii. OA grade IV according Ahlbäck classification.
- iii. Bone marrow cancer like lymphoma.
- iv. Severe anemia.
- v. Active infections.
- vi. Pregnant patients.
- vii. Immune diseases such as Rheumatoid arthritis, gout or pseudogout arthritis, psoriasis.
- viii. Bone diseases such as Kahler and Paget.
- ix. Corticoesteroid and hyaluronic injections within the last 3 months.
- x. Knee surgery in the last 6 months.

3. Ethical considerations

- a. All patients will be informed of the study aims and have the choice to complete an informed consent.
- b. All patients will be informed about alternative treatments.
- c. This study will be approved by the Ethical Committee of Catholic University of Santiago de Guayaquil (UCSG).

4. Evaluations

a. Pre-Operative:

- i. Complete clinical and orthopedic evaluation.
- ii. Laboratory diagnostic tests (biometrics, coagulation parameters glycemia, and liver, pancreatic, renal and lipid profile).
- iii. Radiological exams: Knee X Rays with weight bearing.
- iv. Magnetic resonance of the knee with cartilage measurement. T2 Map. MRI T2 mapping of the cartilage is a non-invasive functional imaging technique delivering cartography of the T2 relaxation time of the cartilage without any contrast injection. It is sensitive to tissue anisotropy, and provides compositional information on the cartilage collagen network, water content and proteoglycans concentration.

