- v. Application of the WOMAC Questionnaire (Western Ontario and McMaster Universities Osteoarthritis Index)²³. The Index contains 24 questions five items for pain (score range 0–20), two for stiffness (score range 0–8), and 17 for functional limitation (score range 0–68). Individual question responses are assigned a score of between 0 (extreme) and 4 (None). Individual question scores are then summed to form a raw score ranging from 0 (worst) to 96 (best). Finally, raw scores are normalized by multiplying each score by 100/96. This produces a reported WOMAC Score of between 0 (worst) to 100 (best).
- vi. Pain measurement with the Visual Analogue Scale (VAS). Visual analogue scales (VAS) are psychometric measuring instruments designed to document the characteristics of disease-related symptom severity in individual patients and use this to achieve a rapid (statistically measurable and reproducible) classification of symptom severity and disease control.
 - a) Restriction of pain medication. Any NSAID 15 days before procedure; and 12 months after.
- vii. Extracellular Matrix (ECM) preparation 3 weeks prior to procedure. Infiltration with procaine 2% by repolarization of the cell membrane in order to improve ECM at the areas to work.

* Each patient from all groups will receive 2 injections of procaine before the procedure. On week 1 and 3.
- ix. No cortisone injections will be permitted before or even 3 months previous to the procedure.

b. Intra-operative:

- i. Independent of MSC source and in order to know the amount and types of injected MSCs, flow cytometry will be used processing of the cells immediately after extraction and prior to the injection into

the knee. In 2006, the International Society for Cellular Therapy proposed minimal phenotypic criteria for the definition of cultured MSCs: expression of CD73, CD90, and CD105, and lack of CD11b or CD14, CD19 or CD79, CD45, and HLA-DR expression²⁴. It should be noted that the main criteria for MSCs are (1) plastic adhesion; (2) the above described phenotype; and (3) their tri-lineage differentiation potential²⁴.

- ii. *CD90 FITC, CD73 PE, CD105 PerCP-Cy5.5* phenotypic expression are measured regarding quantity and viability for all groups of patients.
- iii. *CD34PE, CD11b PE, CD19 PE, CD45 PE, HLADR PE, lack of phenotypic expression, will be measured.*

c. Post-operative:

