- i. AD-MSC will be joined with BM-MSC in a same syringe for application of the percutaneous injection (AD MSC + BM MSC group) into the affected knee.

7. FOLLOW UP.

All patients will be evaluated measuring scores of the WOMAC (Western Ontario and McMaster Universities Osteoarthritis Index)²³ and the VAS (Visual Analogue Scale), before treatment and then at 1, 3, 6, 9 and 12 months.

STUDY FLOW CHART
MSC IN OA

Patient: _____

STUDY FLOW CHART	VISIT 1	VISIT 2	VISIT 3	VISIT 4	VISIT 5	VISIT 6	VISIT 7	VISIT 8	VISIT 9	VISIT 10
Protocol Concept Sheet	Week 1	Week 2	Week 3	Week 4	Week 6	Month 3	Month 6	Month 9	Month 12	Month 15
Diagnosis	X	X								
Orthopaedic exam	X									
X RAYS		X								
MRI T2 map		X								
Laboratory		X								
Inclusion/Exclusion		X								
Informed Consent		X								
Pre Op Evaluations		X								
VAS		X								
WOMAC		X								
Preparation	X		X							
Randomization				X						
Procedures					X					
BM MSC					X					
AD MSC					X					
Flow Citometry Order					X					
Post Op Evaluations					X					
Sticks removed					X					
VAS						X	X	X	X	
WOMAC						X	X	X	X	
MRI T2 map							X			
Adverse Event Evaluation					X	X	X	X	X	
Results										X

MD. Signature

Date.

[figure not shown]
Figure 2. Clinical Trial MSC/OA Protocol Sheet.

Statistical Analysis.

The sample size is determined using the tool of G*Power VERSION 3.0.10. The parameters are applied for the selected F test, two-way mixed ANOVA (repeated measures, with immediate interaction). Given that none of these approaches have been previously compared, either separately or combined, the calculation was conducted considering a medium effect size ($f=0.25$). We established an error probability α of 0.05 and power of 0.95. We calculated the application of 3 repeated measures, even though 6 measures will be conducted for some variables (i.e., the VAS or WOMAC questionnaire).

Based on this criteria, the sample size would be 54, meaning that each group will consist of 18 individuals. The information previously mentioned is represented in detail in the following table and illustrated in a graph below it.

F tests - ANOVA: Repeated measures, within-between interaction		
Analysis:	A priori: Compute required sample size	
Input:	Effect size f	= 0.25
	α err prob	= 0.05
	Power (1- β err prob)	= 0.95
	Number of groups	= 3
	Repetitions	= 3
	Corr among rep measures	= 0.5
	Nonsphericity correction ϵ	= 1
Output:	Noncentrality parameter λ	= 20.250000

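### As written, the first procaine injection (Week 1) comes before charted consent and screening (Week 2); the protocol also contradicts itself on when preparation starts, so this is probably a drafting error

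*Combined protocol and SAP*

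**What the plan says.** - **Procaine, text.** Section 4.a, item vii, describes procaine infiltration to prepare the extracellular matrix. Its opening sentence places this preparation three weeks ahead of the procedure. The note beneath it reads: "Each patient from all groups will receive 2 injections of procaine before the procedure. On week 1 and 3".
- **Procaine, chart.** In the study flow chart (section 7), whose first columns run "Week 1 Week 2 Week 3 Week 4 Week 6 Month 3", the row "Preparation X X" has its marks under Visit 1 (Week 1) and Visit 3 (Week 3).
- **Consent and screening, chart.** The rows "Informed Consent X" and "Inclusion/Exclusion X" each have their single mark under Visit 2 (Week 2). Before the procedure, laboratory tests, X-rays, MRI, VAS and WOMAC are likewise marked only there.
- **Randomization and procedure, chart.** "Randomization X" is marked at Visit 4 (Week 4) and the procedure at Visit 5 (Week 6).
- **Entry criteria.** Section 2.a lists "All patients who sign a specially prepared informed consent for this clinical trial" and "Minimal VAS pain score of 4".
- **Baseline questionnaires.** The Statistical Analysis section puts them three weeks ahead of the intervention.

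**The concern.** Procaine is given here as a protocol-specified step for every trial patient; nothing in the document describes it as routine care. If staff follow the note in item vii and the chart, the needle comes first and the patient's decision to take part comes afterwards.

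The charted check of the exclusions (active infection, severe anemia and pregnancy among them) and the laboratory panel, which includes coagulation, would also come after the first injection. Anyone who declined or failed screening at Visit 2 would already have been injected for a trial they never entered.

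There is a lesser measurement issue. On the charted dates the qualifying VAS and the baseline VAS/WOMAC fall between the two injections, so they would not be clean pre-preparation values. The direction and size of any effect are unknown.

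**Working it through.** The plan gives no figure to reproduce. The check sets the dated statements side by side.

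| Event | Item vii, note | Item vii, opening | Flow chart | Statistical Analysis |
|---|---|---|---|---|
| Procaine | Weeks 1 and 3 | 3 weeks before procedure | Weeks 1 and 3 | – |
| Consent, eligibility, laboratory | – | – | Week 2 | – |
| Baseline VAS/WOMAC | – | – | Week 2 | 3 weeks before procedure |
| Randomization | – | – | Week 4 | – |
| Procedure | – | – | Week 6 | – |

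**1. Order on the literal reading.** First procaine is Week 1 in two places. Consent and screening are Week 2 in the chart. Gap: 2 − 1 = 1 week, procaine first. The chart gives no visit windows. If the labels are consecutive 7-day weeks (an assumption) and the columns are right, the gap runs from 8 − 7 = 1 day to 14 − 1 = 13 days.

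**2. Could the chart have been misread?** Ten rows stand above the preparation row. Eight of them, from X-rays to WOMAC, are marked only at Visit 2. Diagnosis is marked at Visits 1 and 2, and only the orthopaedic exam is confined to Visit 1. Eight consecutive rows in one column, and a preparation row that matches the prose, make a misaligned table unlikely. The Week 2 date for consent nevertheless rests on the chart alone.

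**3. Extent.** Planned injections: 54 × 2 = 108. Before consent: 54 × 1 = 54. This only restates one of two per patient. Each person who declines or fails at Visit 2 would add one; the document gives no such number.

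**4. The contradiction.** Three weeks before a Week 6 procedure is 6 − 3 = Week 3, which is after the Week 2 consent. That matches the second charted injection but not the first. The Statistical Analysis timing for the questionnaires also gives 6 − 3 = Week 3, whereas the chart puts them 6 − 2 = 4 weeks before the procedure. Taken together, the two three-week statements start preparation and baseline at the same time, with no one-week gap.

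**5. Effect on the comparison.** Weeks 1 and 3 both precede Week 4. The injections are the same in every arm and are given before allocation exists, so neither they nor any losses they cause can depend on the arm.

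**The case against.** The strongest reply is that this is a slip in a rough schedule. Item vii itself begins with a timing that puts preparation after consent. Section 4.a lists laboratory tests, X-rays, WOMAC and VAS ahead of procaine. Signed consent is an entry criterion, section 3 says patients will be informed, and item vii speaks of patients in the groups, which means trial patients.

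The chart is not dependable either. It has no 1-month VAS/WOMAC mark although the text requires that assessment, and it puts what appears to be stitch removal in the same column as the procedure. If the procedure were really at Week 4, then 4 − 3 = Week 1 and both three-week statements would fit the Week 1 start; that is possible but not established. Figures 1 and 2 are not in the copy available and might show the intended order.

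Much of this stands. It makes a drafting error the likelier explanation and leaves the one-week gap to baseline uncertain. It does not settle the order. Section 4.a is an undated list, the consent criterion carries no date, and the opening of item vii is contradicted by its own note and by the chart. Nothing available says that consent or eligibility must come before procaine.

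A reader might infer three stronger things that the document does not support:
- **That the trial intends to inject people without consent.** The consent provisions point the other way.
- **That procaine certainly comes first whatever the actual dates.** That depends on the chart columns and on ignoring the three-week statement.
- **That the treatment comparison is biased.** Preparation is common to all arms and precedes randomization.

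**Conclusion.** The point holds as a scheduling error with consequences for consent and safety, and as an internal contradiction. On the only week-by-week schedule available, one of each patient's two procaine injections falls nominally one week before consent, the eligibility check and laboratory tests. A competing sentence in the same item implies about Week 3, which would be after them.

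The conclusion rests on the chart columns being as printed and on the missing figures not settling the order; confidence is moderate for that reason. Sample size, randomization and the analysis model are unaffected. The effect on baseline VAS/WOMAC is secondary and of unknown size. Even as a drafting error it should be corrected before anyone works from the chart.

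**What to change.** Add one sentence to section 4.a, item vii: no procaine is given until consent is signed and eligibility is confirmed. Then make the week numbers in that item and the chart agree, by one of two routes.

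- **Start procaine after the Visit 2 consent, screening and baseline (preferred).** This moves none of those assessments and is closer to the three-week statement. The dates need care. A first injection at Week 3 with the present two-week spacing puts the second at 3 + 2 = Week 5, after the Week 4 randomization. Either shorten the spacing or move randomization (and, if necessary, the procedure) so that both injections still precede allocation. Baseline then precedes all procaine, so change from baseline would include any procaine effect, in all arms alike.
- **Move consent and the eligibility checks to before the Week 1 injection.** This includes the qualifying VAS, the laboratory tests and, if the OA grade is read from them, the X-rays. It may need an earlier screening contact. If the baseline questionnaires move too, they fall nominally at least 6 − 1 = 5 weeks before the procedure, further from the three weeks in the Statistical Analysis section.

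Under either route, give one baseline questionnaire timing in the Statistical Analysis section and the chart. If the sponsor's figures already show consent first, correct the chart and item vii to match them. The cost is a few chart marks, two text edits and a small shift in dates or one earlier contact.

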
Justification

We wish to demonstrate that the use of with autologous MSCs is effective as a treatment option for knee OA grades, II and III. In a large number of cases it is possible to improve the pain, function and quality of life of patients without the side effects of conventional treatments. In other cases, avoid progression to more severe stages that require joint replacement surgery. This research aims at contributing with a low-cost regenerative technique in order to change the course of the disease and significantly reduce public and private sector expenses generated by conservative and surgical OA treatments.

Main goals

- a. The aim of the present study will be to compare three types of intra-articular injections of MSC populations obtained from two clinically relevant sources: injections containing BM-MSC or AD-MSC or a combination of both of them BM-MSC and AD-MSC, in a randomized non blind clinical trial.
- b. To assess the efficacy and safety of treatment with containing BM-MSC or AD-MSC or a combination of both of them BM-MSC and AD-MSC, in relation to pain, function and quality of life in patients with knee OA.

Hypothesis Testing

H1: The combined use of BM-MSC and AD-MSC is superior for pain management in knee OA, than the use of BMSC or AD-MSC alone.

H0: The combined use of MSC from bone marrow and adipose tissue is not superior to the use of MSC derived solely from bone marrow or solely from adipose tissue in the treatment of pain and function in patients with knee OA.

MATERIALS AND METHODS

1. Study design

The present study will be conducted from June 2020 to December 2021 at the Omnihospital, an affiliated center to the Universidad Católica de Santiago de Guayaquil Ecuador, and the support of the Instituto de Investigación e Innovación de Salud Integral, Medical Faculty of the same University and Maastricht University, The Netherlands. This will be a phase III trial, triple arm randomized open label dose to be conducted as a single intra-articular injection of MSC in 3 groups of patients with the diagnosis of knee OA grade II and III (Ahlbäck classification),²² one receiving BM-MSC other receiving AD-MSC and the other BM-MSC + AD-MSC.

2. Study population

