- i. Pain, function and quality of life will be assessed using VAS and WOMAC scales. All patients will be evaluated before treatment, and at 1, 3, 6, 9 and 12 months.
- ii. Magnetic resonance with T2 Map imaging will be performed at baseline to analyze cartilage damage and at 6 months control. This test allows the early diagnosis of areas of cartilage degeneration. In addition it evaluates the relaxation times of water, collagen and proteoglycans. Sequence to assess the structure of the cartilage²⁵.

5. Randomization.

A randomized non blind clinical trial with active control. For this purpose, the random number generator, found on the RANDOM.ORG ® website (available at <https://www.random.org/integers/>)²⁶ will be used to generate 31 random numbers. Value between 0 and 1. Format: 5 columns.

[figure not shown]

Figure 1: Study Design. W (week), M (month), V (visit), VAS (visual analogue scale), WOMAC (Western Ontario Mc Master University Osteoarthritis Index)

6. Procedures

a. **Stem cell obtaining procedures.**

All the procedures will be performed in the operating rooms of the Omnihospital by [name] and [name], both certified orthopedic surgeons. Both will know about the randomization in order to know the source from which MSCs will be obtained, in an ambulatory procedure under local anesthesia and sedation. Average procedure time to obtain de MSCs will be approximately 75 minutes.

b. **BM-MSc PROCEDURE. GROUP 1**

- i. Bone marrow aspiration will be performed using a standard surgical technique: fluoroscopically guided percutaneous puncture of posterior iliac crest bone.
- ii. A total of 60 ml of blood from bone marrow will be aspirated with a heparinized syringe.
- iii. Attach the heparinized syringe to a 150 um filter. Gentle push the bone marrow through the filter to another syringe.
- iv. Attach 45 degree dispensing tip to filtered bone marrow 60 cc syringe.
- v. Slowly transfer the BMA into the Neogenesis 60 cc kit concentrating device until you have reached the 60 cc mark. Secure the green cap and clear safety cap.
- vi. Centrifugation of Neogenesis 60 cc concentrating device. Match counterbalance for each concentrating devices +/- 1.0g. Spin at 4200 rpm / 2800 rcf for 10 minutes.
- vii. Place the concentrating device on the BPS (Benchtop processing station), secure the device with your right hand and slowly turn the knob with your left hand counterclockwise, until the bone marrow aspirate has reached the bottom of the luer slip fitting.

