This study applies descriptive statistics for determining the frequency and proportions for demographic variables (age, gender, education, and ethnicity) and clinical states (severity of knee osteoarthritis, time with disease, comorbidities). Likewise, for calculating the mean and standard deviation of age, WOMAC scores (and each element of the scale) and VAS.

We utilize the two-way mixed ANOVA to compare the differences of means between treatment groups for each dependent variable (WOMAC scores, VAS, and radiological changes). With respect to the WOMAC scores, not only we will analyze the scores in general, but also each score value of the three different components separately (pain, stiffness, function). The tests will determine if there is an interaction between the dependent variable and the factors (independent variables). The factors will be the type of treatment (between subjects) and time (within subjects). For the type of treatment, it

is categorized into: BMSCS only, AD-MSc only, and BM-MSc and AD-MSc combined.

As for the time factor, this will differ according to the dependent variable held for analysis. For example, the analysis of WOMAC and EAV scores will be evaluated in 6 different periods of time. The patients will be asked to respond to our questionnaires three weeks before the intervention and 1, 3, 6, 9, and 12 months after intervention (surgery). With respect to radiological changes, the T2 mapping MRI will be performed twice before the procedure and again six months later.

To guarantee the reliability of the analysis, we will test the atypical values by utilizing box diagrams and the normality with the method of Shapiro-Wilk. Furthermore, the homogeneity of variations will be evaluated with inferential statistic Levene tests, while the homogeneity of covariances with multivariate statistical Box's M test. Consequently, to comply with the hypothesis sphericity, a Mauchly's test will be conducted. In the case of a violation of an assumption, different tests will be utilized.

Finally, in the case of a treatment complication, there will be mixed lineal models generalized for determining the probability of each intervention. The complications considered in this investigation are pain and hematomas in the surgical place where stem cells were extracted, knee pain, and synovial effusion.

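### The plan does not provide for masked reading of the T2 MRI, the one analysed dependent variable that is not patient-reported and can readily be masked

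*Combined protocol and SAP*

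**What the plan says.** Section 1 (Study design) describes a "triple arm randomized open label dose" trial, and section 5 (Randomization) calls it "A randomized non blind clinical trial with active control". Neither makes an exception for an assessor. Section 6a says of the two operating surgeons: "Both will know about the randomization in order to know the source from which MSCs will be obtained". No one else's knowledge of allocation is described.

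Section 4c ii gives the imaging schedule: "Magnetic resonance with T2 Map imaging will be performed at baseline to analyze cartilage damage and at 6 months control". The study flow chart places the baseline MRI at Visit 2 (Week 2), randomization at Visit 4 (Week 4) and the follow-up MRI at Visit 7 (Month 6).

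The Statistical Analysis section applies the two-way mixed ANOVA "for each dependent variable (WOMAC scores, VAS, and radiological changes"), so T2 is an analysed outcome. WOMAC and VAS come from patients: "The patients will be asked to respond to our questionnaires".

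The documents do not name a T2 reader, a number of readers, a masking rule, a reading order or a method for defining the cartilage regions. The two observers in the inclusion criteria concern the Ahlbäck grade at entry.

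**The concern.** Patients know whether bone marrow, fat or both were taken from them, so VAS and WOMAC could be masked only with sham harvests. T2 images do not have this constraint: they can be coded and measured by someone who knows neither arm nor date. Open-label treatment does not require open-label reading, but the plan does not separate the two.

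Two kinds of knowledge matter, and they threaten different results. Knowing the arm can shift one arm's readings relative to the others and so bias the comparison between arms. Knowing whether a scan is baseline or 6 months can shift the apparent change in every arm. With no untreated arm, nothing else in the design would expose a false improvement of that kind. The plan's stated expectations (H1 favours the combination for pain, and the Conclusions anticipate better cartilage quality) make the direction of such a shift foreseeable.

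**Working it through.** **1. The plan's own figure.** Inputs from the G*Power table in the Statistical Analysis section: f = 0.25, alpha = 0.05, 3 groups, 3 repetitions, correlation 0.5, nonsphericity correction 1.

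- lambda = f² × N × m / (1 − rho) = 0.0625 × 54 × 3 / 0.5 = 20.25, as stated.
- df1 = (3 − 1)(3 − 1) = 4; df2 = (54 − 3)(3 − 1) = 102; power = 0.958.
- At N = 51 power is 0.946, so 54 is the smallest multiple of 3 that reaches 0.95.

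The sample size reproduces. It does not depend on how the scans are read.

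**2. When each scan is exposed.** The baseline scan (Week 2) precedes randomization (Week 4). Read when acquired, it cannot be influenced by arm, because no arm has been assigned. It is exposed to arm knowledge only if it is read later. The 6-month scan is exposed whenever it is read.

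**3. Shift in one arm (reader knows the arm).** Two scans per patient are taken, as in section 4c ii and the flow chart. The treatment-by-time interaction is then a one-way ANOVA on the change, with 3 groups of 18 and df 2 and 51. Let b be the reading shift in one arm, in SDs of the T2 change, with no true effect. The group means are 0, 0 and b, and their mean is b/3.

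- lambda = 18 × [(b/3)² + (b/3)² + (2b/3)²] = 12b².

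**4. Equal shift in all arms (reader knows only the date).** The group differences are zero, so the interaction test stays at 5%. The time effect (df 1 and 51) has lambda = 54b².

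| Assumed shift b | lambda, interaction | False positives, interaction (one arm shifted) | lambda, time | False positives, time effect (all arms shifted) |
|---|---|---|---|---|
| 0 | 0 | 5% | 0 | 5% |
| 0.1 SD | 0.12 | 5.9% | 0.54 | 11% |
| 0.25 SD | 0.75 | 10.7% | 3.375 | 44% |
| 0.5 SD | 3.0 | 30.5% | 13.5 | 95% |

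**5. Cross-check.** A two-sided pairwise t-test with 18 per arm has noncentrality b × √(18/2) = 3b. It gives 11.3% at 0.25 SD and 30.8% at 0.5 SD, close to the interaction test.

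The documents give no T2 standard deviation, reader error or expected change. The values of b are therefore assumptions that show a range; they do not estimate what would happen in this trial.

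**The case against.** The strongest reply is that the plan is silent about the MRI reader. The label in section 5 describes the trial as a whole, and only the surgeons are said to know the allocation. A reader might infer that the plan declares an unmasked T2 reading. It does not, and what can be said is that the safeguard is unspecified. This stands.

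Other limits also stand:

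- **Mechanism.** T2 relaxation time is a quantitative measure. Bias would have to enter through choosing or outlining regions, and the documents do not say whether this is manual or automated. Reader judgement is an assumption.
- **Scan date.** A reader might infer that knowing the date spoils the comparison between arms. A shift common to all arms cancels in the interaction, which the plan uses to compare treatments. Only the time effect is at risk.
- **Uniqueness.** It is tempting to call T2 the only outcome that can be masked. That holds among the three dependent variables. However, the Statistical Analysis section also says: "The complications considered in this investigation are pain and hematomas in the surgical place where stem cells were extracted, knee pain, and synovial effusion". Synovial effusion could likewise be judged by a masked assessor.
- **Role of T2.** A reader might treat T2 as the check that confirms the open-label pain scores. The plan gives it no such role. Section 4a describes it as information on cartilage composition, and the hypotheses concern pain and function.
- **Size.** Small shifts do little: at 0.1 SD the interaction test's error rate is about 6%.

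None of this supplies the missing provision. An analysed outcome that could readily be masked still has no masking rule in a trial described as non-blind throughout.

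**Conclusion.** The point holds as a missing safeguard that is cheap to add. Masked T2 reading is not provided for, and without it the 6-month reading, and through it the comparison between arms, could be biased by knowledge of the arm. Under assumed one-arm shifts of 0.1, 0.25 and 0.5 SD, the interaction test's false-positive rate is about 6%, 11% and 30.5% instead of 5%. Knowledge of the scan date threatens the before-after change instead (11%, 44% and 95% for the time effect under the same assumed shifts).

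These figures rest on reader judgement in region placement, 18 evaluable patients per arm, two scans each and no true effect. The point does not invalidate the trial: H1 concerns pain, and the sample size is unaffected. It should be settled before scans are read, because an unmasked reading is hard to undo.

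**What to change.** Add to section 4c ii that, for the outcome analysis, the baseline and 6-month T2 scans are coded with name, arm and date removed, that the same reader measures them in random order, and that the code is broken only after all readings are locked.

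The cost is coding 54 × 2 = 108 image sets and having T2 results later, because scans are read in batches. Section 4a iv lists the baseline MRI with cartilage measurement as a pre-operative evaluation. If those scans were already measured for that purpose, they need a second, research reading under code. No extra reader, scan, visit or patient is needed.

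### The randomization paragraph (31 numbers between 0 and 1) cannot, as written, produce the planned 54 allocations to three arms of 18, and no arm coding or concealment step is stated

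*Combined protocol and SAP*

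**What the plan says.** Section 5 (Randomization) is the only readable account of how allocations are made. It names "the random number generator, found on the RANDOM.ORG ® website", cites the page whose address ends in /integers/, and says it "will be used to generate 31 random numbers. Value between 0 and 1. Format: 5 columns".

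The rest of the document describes a different list:

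- Section 1 (Study design) calls the trial "triple arm randomized open label".
- Section 2 (Study population): "A total of 54 patients with the diagnosis of knee OA grade II and III will be recruited", with 18 assigned to each of Groups 1, 2 and 3.
- Statistical Analysis, sample size: "the sample size would be 54, meaning that each group will consist of 18 individuals".
- Statistical Analysis, treatment factor: "BMSCS only, AD-MSc only, and BM-MSc and AD-MSc combined".

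On who knows the allocation, section 6.a says of the two operating surgeons: "Both will know about the randomization in order to know the source from which MSCs will be obtained". The study flow chart in section 7 puts eligibility, consent and the baseline VAS and WOMAC at Visit 2, and randomization at Visit 4.

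**The concern.** Every between-arm comparison in the Statistical Analysis section rests on the allocation list. Staff who follow section 5 literally would have too few numbers. On the natural reading of an integer generator, they would also have too few codes. They would then have to improvise, and the document gives no rule for doing so.

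The stake is selection bias. In an open-label trial, concealing the next assignment until the patient is committed is the main protection against steering patients between arms, because nothing is masked afterwards. The main outcomes, VAS and WOMAC, are reported by unblinded patients, so secure allocation matters all the more. Section 6.a tells us that the surgeons know the allocation. It does not say when they learn it or whether they see the whole list.

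**Working it through.** **Inputs**

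| Quantity | Value | Where |
|---|---|---|
| Patients | 54 | Section 2; Statistical Analysis |
| Arms and sizes | 3 × 18 | Section 2; Statistical Analysis |
| Random numbers | 31 | Section 5 |
| Range of values | 0 to 1, integer page | Section 5 |
| Sample-size inputs | f = 0.25, α = 0.05, power 0.95, 3 groups, 3 repetitions, correlation 0.5, ε = 1 | Statistical Analysis |

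**1. Is 54 itself the slip?** For the within-between interaction in a repeated-measures ANOVA with k groups and m repetitions:

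- λ = f² × N × m × ε / (1 − ρ) = 0.0625 × 54 × 3 × 1 / 0.5 = 20.25, which matches the plan's output.
- df1 = (k − 1)(m − 1) = 4; df2 = (N − k)(m − 1) = 51 × 2 = 102.
- Power from the noncentral F is 0.958. At N = 51 it is 0.946. The smallest N reaching 0.95 is 52, and the smallest multiple of 3 is 54.

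So 54 is reproduced and agrees throughout the document. The figure out of line is 31.

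**2. Count.** At one number per patient, 54 − 31 = 23 patients have no number, and 23/54 = 42.6%. This does not depend on whether the values are integers or decimals. Nor is 31 divisible by 3, so a list of that length could not give three equal arms.

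**3. Coding, integer reading.** The values 0 and 1 are two codes for three arms. Drawing 23 more numbers with the same setting mends the count but not the coding. Pooling the digits does not help either:

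- 31 binary digits give 2³¹ ≈ 2.1 × 10⁹ sequences.
- There are 54!/(18!)³ ≈ 8.8 × 10²³ balanced lists.
- Even randomly ordered blocks of three allow 6¹⁸ ≈ 1.0 × 10¹⁴ lists.

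**4. Coding, decimal reading.** Cutting the interval at thirds would code three arms, but there would still be only 31 allocations. With a full 54 unrestricted draws, P(18/18/18) = 54!/[(18!)³ × 3⁵⁴] = 0.0151. A restriction rule would be needed to give the planned arm sizes, and none is stated.

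**5. Other schemes.** One decimal choosing the order within each block of three would work and would need 54/3 = 18 numbers. The document does not describe this, and 18 is not 31.

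**6. Concealment.** The readable text names no holder of the list, no envelopes or central release, and no limit on who sees upcoming assignments. The flow chart gives the timing of randomization, which is not the same thing.

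**The case against.** **The missing figures may hold the detail.** Figure 1 directly follows the randomization paragraph and is titled as the study design. The terms in its caption are an abbreviation key, so the absence of arm names there is weak evidence about its content. Figure 2 is also not shown. This stands against the claim that no number-to-arm key exists, which can only be made about the readable text. A key in a figure would still leave 31 numbers against 54 patients in the text.

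**The 0.0151 probability sounds worse than it is.** It needs a decimal reading, equal cut-points and 54 numbers, none of which is stated. Unequal arms also cost little. Under simple 1:1:1 allocation of 54, simulation gives a mean variance inflation for pairwise comparisons of about 4%, and about 13% at the 95th percentile. Dividing λ = 20.25 by 1.04 and 1.13 takes power from 0.958 to about 0.950 and 0.93. This stands: the figure shows that nothing stated delivers the planned 18 per arm, not that imbalance would do serious harm.

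**Selection bias is inferred.** The surgeons must know the cell source in order to harvest, so their knowledge is no proof of failed concealment. Eligibility, consent and baseline scores precede randomization, and two observers grade the OA. The document does not say who enrols. All of this is right and limits the room for steering without removing it. The concealment gap is an omission, and so a weaker point than the contradiction in the numbers.

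**The error would reveal itself.** A 0/1 list cannot label a third arm, so someone would have to change it before use. That is likely, but an undocumented repair is the very risk at issue.

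**Conclusion.** The concern holds. Section 5 conflicts with the planned size and structure of the trial and has to be corrected. At one number per patient, 23 of 54 patients (43%) have no allocation. On the integer reading, which the cited page address supports, two codes must serve three arms whatever the count. On the decimal reading the coding problem can be solved, but the shortfall remains and no rule gives 18 per arm. No readable passage reconciles these.

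The missing arm key and concealment step are a separate specification gap, limited to the readable text because two figures are absent. Selection bias is a risk that follows from the gap; the documents do not show that it has occurred.

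**What to change.** Replace the paragraph in section 5 with text to this effect:

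> Before first enrolment, one list of 54 allocations is generated as a random permutation of three labels (BM-MSC, AD-MSC, BM-MSC + AD-MSC), exactly 18 each. An existing study member who neither enrols nor operates holds the list. Each assignment is released singly at Visit 4, after the Visit 2 eligibility, consent and baseline entries are complete. The operating surgeons learn only the current patient's assignment.

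A single permutation has two small weaknesses. The arms may be uneven if recruitment stops early. Also, surgeons who have seen every past assignment could predict the end of the list: the last 1 + 17/37 ≈ 1.46 allocations are determined on average. If balance over time is wanted, use permuted blocks of undisclosed, varying size instead (multiples of 3 totalling 54). These limit the first weakness and, compared with a fixed block size, make upcoming assignments harder to guess.

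If allocation has already begun, the sponsor should document the method actually used.

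The cost is one protocol paragraph, one 54-line list and minor work for its holder; the documents do not say who is available for that. No extra patients or visits are needed.
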